Title: Endocrine, Metabolic and Microbiome Influence on the Post-COVID Syndrome

Principal Investigator: [name]., Internal Medicine, UTMB

Co-I: [name]., Internal Medicine, UTMB

Co-I: [name]., Pediatrics, UTMB

Co-I: [name], Ph.D., Internal Medicine, UTMB

Co-I: [name]., Internal Medicine, UTMB

Co-I: [name]., Internal Medicine, UTMB

Co-I: [name]., Internal Medicine, UTMB & Health and Kinesiology, TAMU

Institutions: The University of Texas Medical Branch at Galveston (UTMB)

Texas A&M University (TAMU)

Background and Significance

The onset of the COVID-19 pandemic has led to a subset of patients that, once recovered from the acute infection, also experience an intractable and debilitating set of lingering symptoms termed post-COVID syndrome, also known as post-acute sequelae of SARS CoV-2 (PASC). The most common symptoms include anxiety, shortness of breath, continued loss of the sense of smell and taste, loss of appetite with subsequent weight loss, sleep difficulties, severe fatigue, cognitive dysfunction (foggy brain) and increased frailty. These patients frequently present to the emergency room looking for symptom management because they are unable to perform normal activities of daily living and maintain job performance. The mechanisms behind this syndrome have proven elusive because patients symptom severity and treatment regimen including different requirements for hospitalization, supplemental oxygen, dexamethasone and remdesivir. Thus, it is critical to characterize the baseline endocrine, metabolic, inflammatory and microbiome alterations in PASC patients to better identify and manage the symptoms to prevent potential long-term health consequences.

UTMB has established a post-COVID clinic for management of PASC patients, but it is recognized that a more complete clinical picture of the underlying mechanisms driving these lingering symptoms is needed. UTMB's post-COVID clinic has seen over 150 patients to date with a waiting list of over 200 patients who wish to be treated. Thus, it is clear that there is great demand for understanding the mechanisms and potential treatments for the long-term debilitating effects of PASC.

Persistent and long-lasting health problems are common in patients after COVID-19 infection. In a recent study of patients that had been hospitalized with COVID-19, two months after discharge, 87% reported at least one lingering symptom (joint pain, fatigue, breathing issues, etc), more than 50% reported

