- **The Beck Depression Inventory-II (BDI-II)** is one of the most widely used self-report inventories to assess depressive symptom severity in adolescent and adult populations (clinical and non-clinical). The BDI-II is comprised of 21 individual items reflecting specific cognitive, affective, and physical symptoms of depression. Each item includes four statements that vary in the description of symptom of severity. Scores range from 0 to 3, with a score of "3" indicating a severe symptoms and a score of "0" indicating an absence of concern with that particular aspect of depressive symptomatology. The total score is the sum of all endorsed statements. If more than one statement from a given item is chosen by the respondent, only the statement of greatest severity is scored. The maximum total score is 63. The BDI-II Manual designates the following raw score classifications depression severity: ≤ 13 = *minimal*; 14-19 = *mild*; 20-28 = *moderate*; ≥ 29 = *severe*.
- **Gastrointestinal Symptom Rating Scale (GSRS)**. Gastrointestinal symptoms will be monitored using the 15-item GSRS. Each question has a seven-point Likert-type scale where 1 represents absence of symptoms and 7 represents very troublesome symptoms.

PASC Subjects

Interested subjects with a previous diagnosis of COVID will undergo a phone pre-screen including the Brief Fatigue Inventory (BFI) questions 1-3. If they score ≥ 3 on any BFI questions 1-3, and are interested in participating in the study, they will be scheduled for a formal consenting and medical screening at the UTMB Clinical Research Center (CRC). Subjects will report to the UTMB

Institute for Translational Sciences (ITS) Clinical Research Center (CRC) for the medical screening and then for three separate study visits (Visits A, B and C). The study visits will consist of measurement of glucose tolerance, growth hormone and cortisol production, resting energy expenditure, functional testing including hand grip strength, gait measurements and 6 minute walk test, fatigue measurements, cognitive function assessment and questionnaires of health status, mood and quality of life, diet, sleep, and gastrointestinal health. Blood sampling for measurement

of amino acid levels, hormones, and metabolites will be drawn. In addition, fecal and oral samples will be collected for analysis of the GI and oral microbiomes. Visits A, B and C will be at least 7 days apart. All in person visits we will follow UTMB in-person procedures for safety.

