- Indirect calorimetry for Resting Energy Expenditure (REE). Expired gases will be collected and analyzed for O₂ and CO₂ concentrations for the determination of energy expenditure and substrate oxidation in subjects using the ITS-CRC indirect calorimetry system, Vmax Encore, Carefusion. The subject will be asked to lie down on a bed and the ventilated canopy hood will be placed over their head and shoulders. The room will be darkened and external noises will be eliminated, as much as possible. The subject will be asked to relax and remain awake but as still as possible for the testing period of 30 minutes.
- ATCH (Cortrosyn) stimulation test. Subjects will have an ATCH stimulation test. 3.5 ml of blood will be collected using a butterfly needle from a peripheral vein in the arm for the baseline (time: 0 minutes) and analyzed for levels of cortisol. 0.25 mg Cortrosyn (1 vial) will be injected IM in the deltoid muscle of the subject. And additional blood samples (3.5 mL) will be collected at 30 and 60 minutes after the injection to test for levels of cortisol. All blood samples will be sent to UTMB clinical laboratory for analysis and entered into subjects UTMB medical chart.
- Phlebotomy. Subjects will have a catheter placed into a peripheral vein in their arm (0.9% sodium chloride set at TKO) for the ATCH stimulation test. The IV will be discontinued when testing is complete.
- Cognitive Assessment. Subjects will undergo a cognitive assessment.

Montreal Cognitive Assessment (MoCA). The Montreal Cognitive Assessment (MoCA) is a rapid assessment of cognition. The MoCA consists of 9 questions with the following subcategories: visuospatial/executive, naming, memory, language, abstraction, delayed

recall and orientation. The MoCA has been used extensively to detect cognitive impairment in many conditions, including head trauma. Version 8.1 will be used.

- Modified 6-minute walk. Walking performance will be assessed in subjects during 6 minutes of walking in long corridor hallways. This is a standard test of walking performance that has been validated in similar studies. Subjects will be asked to walk at a 100% effort. Distance traveled for each 2-minute category will be recorded, as well as total distance.
- Questionnaires. Questionnaires will be completed to assess perceptual fatigue, symptoms associated with growth hormone deficiency, depression, and gastrointestinal symptoms.

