 - **Multidimensional Fatigue Symptom Inventory (MFSI)** will also be used to measure perceptual fatigue. Fatigue symptoms will be measured using the 30-item Multidimensional Fatigue Symptom Inventory – Short Form, a validated measure that yields one overall score of total fatigue (range -24-96, with higher scores indicating more fatigue) and five subscales (general, physical, emotional, mental, vigor). With the exception of the vigor subscale, higher scores indicate greater fatigue.
 - **Assessment of Growth Hormone Deficiency in Adults (QoL-AGHDA)** Symptoms of growth hormone deficiency will be measured in subjects using the QoL-AGHDA. This 25-item questionnaire measures specific symptoms associated with growth hormone deficiency, with a score range of 0 to 25, with a higher score indicating worse symptoms.
 - **The Beck Depression Inventory-II (BDI-II)** is one of the most widely used self-report inventories to assess depressive symptom severity in adolescent and adult populations (clinical and non-clinical). The BDI-II is comprised of 21 individual items reflecting specific cognitive, affective, and physical symptoms of depression. Each item includes four statements that vary in the description of symptom of severity. Scores range from 0 to 3, with a score of "3" indicating a severe symptoms and a score of "0" indicating an absence of concern with that particular aspect of depressive symptomatology. The total score is the sum of all endorsed statements. If more than one statement from a given item is chosen by the respondent, only the statement of greatest severity is scored. The maximum total score is 63. The BDI-II Manual designates the following raw score classifications depression severity: ≤ 13 = *minimal*; 14-19 = *mild*; 20-28 = *moderate*; ≥ 29 = *severe*.

[figure not shown]
Statistical Considerations

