3. Significant heart, liver, kidney, blood or respiratory disease as determined by Principal Investigator.
4. Uncontrolled diabetes mellitus.
5. Any history of a recently (12 months) diagnosed cancer other than a skin cancer (excluding melanoma).
6. Current alcohol or drug abuse.
7. History of psychosis.

8. Pregnancy or become pregnant during the trial.
9. Subjects who are being managed with narcotics will be excluded as the effects of central nervous system depressants may interfere with study test results.
10. Other medical condition or medication administration deemed exclusionary by the study investigators.

PASC subjects

Inclusion criteria

1. Male or female with a history of COVID with diagnosis confirmed by PCR test.
2. Minimum of 6 months since diagnosis of COVID by PCR test.
3. Ages 18 to 80 years.
4. Score of 3 or higher on any question 1-3 of the Brief Fatigue Inventory (BFI) questionnaire.
5. Participant is willing and able to give informed consent for participation in the study.

Exclusion criteria

1. Current COVID infection.
2. Unable to walk unassisted.
3. Significant heart, liver, kidney, blood or respiratory disease as determined by Principal Investigator.
4. Uncontrolled diabetes mellitus.
5. Any history of a recently (12 months) diagnosed cancer other than a skin cancer (excluding melanoma).
6. Current alcohol or drug abuse.
7. History of psychosis.
8. Pregnancy or become pregnant during the trial.
9. Subjects who are being managed with narcotics will be excluded as the effects of central nervous system depressants may interfere with study test results.
10. Other medical condition or medication administration deemed exclusionary by the study investigators.

Sources of materials. We may obtain blood, urine, fecal, saliva and questionnaire data from the subjects. All data/samples will be collected solely for the purpose of experimentation. The blood will be used for screening and to measure metabolites, amino acids, hormones and measures of inflammation. Fecal, nasal and saliva samples will be used for determination of the GI, nasal and oral microbiomes. Questionnaire data will be used to assess quality of life.

Recruitment Methods and Consenting Process

- a) Potential subjects may be patients of the investigators.
- b) 1. PASC subjects may be recruited from the UTMB post COVID clinic in one of the following ways:

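### The BDI-II total counts physical symptoms, and only PASC subjects are selected on fatigue, so a PASC versus non-PASC comparison of that total may overstate depression in PASC

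*Combined protocol and SAP*

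**What the plan says.** The BDI-II is given to non-PASC controls at Visit A and to PASC subjects at Visit C. Both questionnaire sections describe it in the same way: "The BDI-II is comprised of 21 individual items reflecting specific cognitive, affective, and physical symptoms of depression". On scoring they say "The total score is the sum of all endorsed statements", and "The maximum total score is 63". Severity bands follow, introduced by "The BDI-II Manual designates the following raw score classifications depression severity": minimal up to 13, mild 14 to 19, moderate 20 to 28, severe from 29. No sub-score is described.

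PASC inclusion criterion 4 is "Score of 3 or higher on any question 1-3 of the Brief Fatigue Inventory (BFI) questionnaire". The inclusion and exclusion criteria for non-PASC controls contain no fatigue item. Background and Significance lists, among the most common symptoms of the syndrome, "loss of appetite with subsequent weight loss, sleep difficulties, severe fatigue, cognitive dysfunction (foggy brain) and increased frailty".

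The Visit C section states the purpose of the questionnaires: "Questionnaires will be completed to assess perceptual fatigue, symptoms associated with growth hormone deficiency, depression, and gastrointestinal symptoms". Statistical Considerations sends symptom outcomes as a class to an ANOVA model with age and other covariates where possible, and promises multiple testing corrections. It names neither depression nor the BDI-II. The HADS, whose seven depression questions are summed separately from its anxiety questions, is collected in both groups.

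**The concern.** One group is selected on a symptom domain that the outcome scale may itself score. A PASC subject and a control with the same mood could then have different BDI-II totals, because the PASC subject also scores on physical items. This is bias, so more subjects or a multiplicity correction would not remove it.

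A higher BDI-II total in PASC could then be read as depression when some or all of it is the fatigue that defined the group. Links between the BDI-II total and hormones or organisms could carry the same mixture. Two depression scales are collected and no rule says how to read them together, so the choice between them could be made after the results are seen.

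**Working it through.** **The plan's own figure.** 21 items × 3 points = 63, which matches the stated maximum. The documents give no BDI-II mean, SD, effect size or power.

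**What the documents fix**

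| Input | Value | Place |
|---|---|---|
| BDI-II content | 21 items, physical symptoms included | Questionnaires, both groups |
| BDI-II scoring | one sum, no sub-score | Questionnaires, both groups |
| Fatigue entry criterion, PASC | BFI 3 or more on any of questions 1 to 3 | PASC inclusion criterion 4 |
| Fatigue entry criterion, non-PASC | none | non-PASC criteria |
| Group sizes | 32 and 32 | Human Subjects |
| Alpha | 0.05; two-sided in the power statement | Statistical Considerations |

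**What must be assumed.** The number of overlapping items, the points each adds when mood is equal, and the SD of the total. Let s be the shift in the PASC mean total with equal mood. Six items each scoring 1 point higher, or two items each scoring 3 higher, both give s = 6.

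**Formula.** Each group completes the BDI-II at one visit, so a two-sample t-test stands in for the group contrast. Standardised shift d = s / SD; non-centrality = d × √(32/2) = 4d; 62 degrees of freedom; two-sided critical value 2.00. The result is the chance of a significant difference when mood is equal.

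| Assumed shift s | d at SD 8 | SD 6 | SD 8 | SD 10 | SD 12 |
|---|---|---|---|---|---|
| 0 | 0 | 5% | 5% | 5% | 5% |
| 1 | 0.125 | 10% | 8% | 7% | 6% |
| 2 | 0.25 | 26% | 17% | 12% | 10% |
| 4 | 0.50 | 75% | 50% | 35% | 26% |
| 6 | 0.75 | 98% | 84% | 66% | 50% |

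**Multiplicity.** These chances are at unadjusted alpha. The plan promises a correction but does not name the method or the family of tests. If ten tests shared alpha equally (an assumption, 0.05/10 = 0.005), then at SD 8 the 4-point shift falls from 50% to 19% and the 6-point shift from 84% to 54%. The correction makes a false finding rarer but leaves the bias in the estimate.

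**Severity bands.** The minimal and mild bands meet between 13 and 14. A subject with an assumed 8 points from mood is minimal. With an assumed 6 further points from physical items the total is 8 + 6 = 14, which is mild. The example is chosen to show the mechanism and says nothing about how often it would happen.

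**The case against.** The strongest reply is that the plan never sets out a depression comparison between these groups. Aim 2 names fatigue, sleep and cognition. Aim 3 compares PASC with the BIAFAC database and normal controls. The non-PASC COVID group appears only in Aim 4, on the microbiome, and Human Subjects justifies adding it on microbiome grounds. This stands: a PASC versus non-PASC test of the BDI-II arises only through the general model for symptom outcomes. The point is therefore conditional on that use.

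A reader might also infer that the severity bands will be reported as the prevalence of depression in PASC. The documents do not support that. They describe the manual's bands and do not say that these will be tabulated or compared.

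Nor do the documents list the BDI-II items or say that any of them measures fatigue, sleep or appetite. The overlap is inferred from the words on physical symptoms. Controls have no upper limit on fatigue, so some of them may carry the same load. In the BIAFAC comparison that Aim 3 does name, fatigue is present in both groups and no direction of bias follows.

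Finally, depression does not rest on the BDI-II alone. HADS depression, SF-36 emotional wellbeing and the MFSI emotional subscale are collected in both groups. That lessens the problem but does not settle it: no rule says how these scores are to be read together, and the documents do not say that the HADS depression questions are free of physical symptoms.

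**Conclusion.** The concern holds as a risk: a PASC versus non-PASC comparison of the BDI-II total may overstate depression in PASC. The documents establish a total that includes physical symptoms, selection on fatigue in one group only, and no sub-score or rule to separate the two.

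A reader might conclude that the total will overstate depression, or that a false finding is likely. Neither follows. With 32 per group, SD 8 and unadjusted alpha 0.05, the illustrative chance of a significant difference with equal mood runs from 8% at 1 point to 84% at 6 points; with SD between 6 and 12 it runs from 6% to 98%. Every shift and SD here is assumed, so the effect could be negligible or decisive. As depression is in no aim, this is an inexpensive improvement to interpretation and not a flaw in the main design.

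**What to change.** Keep the BDI-II total and add a short statement to Statistical Considerations:

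- Any PASC versus non-PASC comparison of depression will report, beside the BDI-II total, the sum of its cognitive and affective items without the physical items, with the item split taken from the instrument's manual and fixed before the data are examined.
- The same comparison will report the HADS depression subscale.
- A group difference will be attributed to depression only if it is also seen without the physical items.
- If the BDI-II severity bands are tabulated, a note will say that they may be inflated by fatigue in the PASC group.

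The cost is wording and two further results in a table, with no new visits, samples or subjects. There are two downsides. The reduced score has no severity cut-offs in the protocol, so it is reported as a score only. Item-level BDI-II responses must be retained, and the protocol does not state that they will be.

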Notably, the cluster of symptoms associated with PASC include profound fatigue and cognitive dysfunction, which are strikingly consistent with a syndrome that our clinical research team has described in patients after traumatic brain injury (TBI) designated BIAFAC (Brain Injury Associated Fatigue and Altered Cognition). Over the last 12 months we have reported the characteristics of BIAFAC syndrome (Urban 2020; Yuen et al. 2020). In particular, TBI patients with BIAFAC present with lingering and profoundly debilitating symptoms including severe fatigue, cognitive dysfunction (foggy brain), sleep disturbances, and the inability to perform activities of daily living that persist for years post-injury. Mechanistically we have explored the role of the gut microbiome discovering altered communities in TBI patients in long-term care facilities compared with controls (Urban et al. 2020). We also established that many TBI patients with BIAFAC also present with abnormal growth hormone (GH) secretion, and when treated with recombinant GH, a majority of patients have significant improvement of both fatigue and impaired cognition (Wright et al. 2020). While studies are underway to understand the details of the mechanism causing BIAFAC and why GH treatment alleviates symptoms in these patients, we are intrigued that the symptom phenotype of PASC patients overlaps with many BIAFAC symptoms. It is possible that PASC symptoms may be addressed through similar treatment strategies including the potential for prebiotic/probiotic enhancement of microbiome health.

In the current pilot proposal, we will characterize the baseline endocrine, metabolic, inflammatory and gut microbiome alterations in PASC patients and compare those to our extensive database of BIAFAC patients and normal controls. From this critical baseline data, we will develop carefully defined clinical research trials that will test potential treatments for alleviating the syndrome. We **hypothesize** that an imbalanced endocrine axis stemming from COVID infection leads to metabolic, inflammatory and microbial dysregulation resulting in the onset of persistent PASC symptoms.

Specific Aims

Specific Aim 1: Characterize baseline measures of endocrine function, metabolism, inflammation, and composition of the gut and nasal microbiome of patients reporting PASC symptoms.

Specific Aim 2: Assess neuropsychological measures of fatigue, sleep, and cognition for patients reporting PASC symptoms.

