Specific Aim 3: Compare physiological and neuropsychological measures of PASC patients to our extensive database of BIAFAC patients and normal controls.

Specific Aim 4: Characterize the microbiome of PASC patients and compare to: a)our database of healthy control subjects, b) our database of symptomatic BIAFAC patients, c) new collected samples of patients with a history of COVID who did not develop PASC.

Experimental Design and Methods

Subjects. We will study subjects (aged 18 - 80 years) with a history of COVID (n=16M/16F) that have been seen in the UTMB COVID clinic for ongoing symptom management and subjects (aged 18 – 80 years) with a history of COVID (n=16M/16F) who did not develop PASC. Potentially eligible patients may also self-refer to the study from surrounding post-COVID clinics or clinicaltrials.gov. Subjects with a history of COVID and no PASC will be recruited by placement of flyers around the community as well as through UTMB announcements.

[figure not shown]
(See *Protection of Human Subjects - Recruitment Methods and Consenting Process for detailed information regarding recruitment and consenting*).

COVID non-PASC Control Subjects

Interested subjects with a previous diagnosis of COVID without a history of PASC will undergo a phone pre-screen. If they are interested, they will be scheduled for a formal consenting and medical screening at the UTMB Clinical Research Center (CRC). Subjects will report to the UTMB Institute for Translational Sciences (ITS) Clinical Research Center (CRC) for the medical screening and one study visit. The study visit will consist of a glucagon stimulation test (GST) to assess growth hormone status; questionnaires assessing health status, mood and quality of life, diet, sleep, and gastrointestinal health. Blood samples will be drawn to measure amino acid levels, hormones, and metabolites. Fecal samples will be collected to analyze the GI microbiome.

Screening Procedures: All subjects consenting will undergo the following procedures. Screenings will take place at the UTMB ITS Clinical Research Center (ITS-CRC).

- Vital signs. Vital signs will be collected at screening. This will include height, weight, blood pressure, pulse, respirations, and temperature.
- Urine Screening Labs. Urine will be collected at screening and sent to the UTMB clinical laboratory for basic urinalysis. Results will be entered into the UTMB medical chart.
 - Urinalysis

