In this observational study we intend to compare the microbiome community structures from the GI tract (fecal microbiome), oral, vaginal, and nasal mucosa sites in COVID long-haulers (subjects that meet our criteria for fatigue, altered cognition and are post-COVID-19) to community structures from our in house data as well as those published by others including the human microbiome project consortium. The observational hypothesis is that PASC subjects may have notable differences from normal subjects associated with the PASC sequelae described above. The study design is based on our past experiences with brain injury associated fatigue and altered cognition (BIAFAC) syndrome leading us to make practical group size selections of 32 symptomatic PASC patients. The design will include equal numbers of males and females (n=16 each). Because no publications are currently available describing changes to the microbiome in PASC patients, we are unable to complete specific power calculations. However, based on our previous clinical studies of BIAFAC patients with similar symptom presentation, we anticipate that

we would need 6 subjects per group to have an 80% probability of detecting significant differences in at least one of the previously identified BIAFAC organisms (two-sided, $\alpha=0.05$). With the proposed subject numbers (n=32 completed subjects) we believe we will generate reasonable preliminary findings to identify differences in microbiome communities related to detection and/or abundance of specific organisms associated with specific PASC symptoms.

For quantifiable outcomes such as abundances of individual species in the GI microbiome and symptom related outcomes, a standard repeated measure ANOVA model will be used. When possible, age and other covariates will be brought into the model to account for individual variability and group differences. Significance tests will be performed at the $\alpha=0.05$ level, and multiple testing corrections will be used to account for potential Type I error rate inflation. Nonparametric, generalized linear, and transformed response models will be considered as necessary to alter the model to account for deviations from standard assumptions (normality, linearity, etc.). Current data support statistical outcomes being established with group sizes similar or slightly larger than our previous BIAFAC studies.

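### The statistical section describes the PASC group by fatigue and altered cognition, but the listed criteria require only a fatigue score, with no cognition criterion and no requirement that the fatigue began or worsened after COVID

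*Combined protocol and SAP*

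**What the plan says.** - **Statistical Considerations, first paragraph**, describes the compared subjects as "COVID long-haulers (subjects that meet our criteria for fatigue, altered cognition and are post-COVID-19".
- **PASC subjects, Inclusion criteria**, has five items: PCR-confirmed COVID, at least 6 months since that diagnosis, age 18 to 80, consent, and one symptom item: "Score of 3 or higher on any question 1-3 of the Brief Fatigue Inventory (BFI) questionnaire".
- **Experimental Design, PASC Subjects**, describes the entry step: "Interested subjects with a previous diagnosis of COVID will undergo a phone pre-screen including the Brief Fatigue Inventory (BFI) questions 1-3". The threshold is again 3.
- **Visit C, Cognitive Assessment**, is where cognition is first tested: "The Montreal Cognitive Assessment (MoCA) is a rapid assessment of cognition". No cut-off is given. Specific Aim 2 makes cognition something to be studied: "Assess neuropsychological measures of fatigue, sleep, and cognition for patients reporting PASC symptoms".
- **Background** describes the intended population as people who "once recovered from the acute infection, also experience an intractable and debilitating set of lingering symptoms termed post-COVID syndrome". The Subjects paragraph refers to patients "that have been seen in the UTMB COVID clinic for ongoing symptom management", then adds: "Potentially eligible patients may also self-refer to the study from surrounding post-COVID clinics or clinicaltrials.gov". Recruitment Methods, item b) 3, and Recruitment and informed consent, item 2, extend self-referral to flyers and UTMB announcements.

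**The concern.** There are two separate problems.

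**Mismatch.** The statistical section refers to criteria for altered cognition, but the documents list none. This is more than wording. The same section borrows its power basis from BIAFAC patients on the ground that they present similarly, and BIAFAC is by its name fatigue with altered cognition.

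**Onset.** The hypothesis is that COVID infection sets off the dysregulation behind persistent symptoms. No listed criterion links the fatigue to the infection: the 6-month rule dates the infection, not the symptom. A person with long-standing fatigue of another cause and an old positive PCR test meets every listed PASC inclusion criterion.

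What is at stake is the meaning of the group label. A difference between this group and the COVID-recovered controls (Aim 4c) might be weakened by subjects whose fatigue has another origin. It might also be produced by them and then reported as a feature of PASC. The protocol says later trials will be developed from these baseline data, so the label carries forward.

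**Working it through.** **1. Group definition, side by side**

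| Element | Statistical Considerations | PASC inclusion list and described pre-screen |
|---|---|---|
| Fatigue | required | BFI 3 or more on any of questions 1-3 |
| Altered cognition | required | absent; MoCA only at Visit C, no cut-off |
| After COVID | required | infection at least 6 months ago |
| Fatigue began or worsened after COVID | not stated | absent |

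**2. Could another provision supply the onset rule?** The screening history and physical states no such rule, and a clinical history from the past 3 months may replace it. Exclusion 10 is investigator discretion. Pre-COVID versus current ratings are planned for ADL and PSQI, but not for fatigue, and they are not entry criteria. Clinic recruitment narrows the gap, but self-referral means clinic attendance is not required.

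**3. The plan's own power figures.** These are background only and are not disputed. For a two-sample t test with n per group, the noncentrality is d × √(n/2) with 2n − 2 degrees of freedom. With the stated d = 1.184 and two-sided alpha 0.05, power at 10/15/20/25 per group is 70.7/87.9/95.4/98.4%, which matches the *Alistipes onderdonkii* row exactly. Solving the 10-per-group column for Odoribacter (52.5%) gives d = 0.956. That value reproduces the rest of its row (71.5/83.8/91.2%).

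**4. Illustration for Aim 4c, 32 versus 32.** The documents give no misclassification rate, so m = 0/10/20/30% is assumed. Suppose misclassified subjects differ from controls by k times the true PASC difference. Then

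effect = d × (1 − m + m·k); noncentrality = effect × √(32/2) = 4 × effect; df = 62; critical t = 1.999.

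Odoribacter, d = 0.956, uncorrected alpha 0.05:

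| m | Effect at k=0 | Noncentrality at k=0 | Power, k=0 (resemble controls) | Power, k=1 | Power, k=2 |
|---|---|---|---|---|---|
| 0 | 0.956 | 3.824 | 96.4% | 96.4% | 96.4% |
| 10% | 0.860 | 3.442 | 92.3% | 96.4% | 98.5% |
| 20% | 0.765 | 3.059 | 85.3% | 96.4% | 99.5% |
| 30% | 0.669 | 2.677 | 75.0% | 96.4% | 99.8% |

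These figures assume equal variances. Simulating the mixed group directly (200,000 runs) lowers the k=0 values slightly, to about 91/83/71%.

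**5. Opposite case.** PASC has no effect on an organism, but misclassified subjects differ by 1.184 SD. Each of the 32 PASC subjects is drawn from N(1.184, 1) with probability m and otherwise from N(0, 1); controls are N(0, 1). Simulated rejection at uncorrected alpha 0.05 is about 7/14/25% for m = 10/20/30%, against 5% at m = 0. A simple mean shift of 1.184 × m gives 7.5/15.4/28.8%. That is too high, because it omits the mixture's extra variance, m(1 − m) × 1.184² (at 30%: 0.21 × 1.402 = 0.294).

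**The case against.** The other side has a reasonable case.

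- **The mismatch is one parenthesis.** If cognition was never meant as an entry condition, correcting it changes no enrolment or data. That stands for the first problem, though the sections still need to agree.
- **The documents repeatedly signal the intended population, and the clinic is large enough to supply it.** It had seen over 150 patients, with over 200 waiting, against a need for 32. This makes a large misclassified share less likely, but it sets no rule for those who self-refer.
- **The pre-screen is described as including the BFI questions, and a separate pre-screening sheet is cited.** A reader might infer that onset is never asked. The documents do not support that: the sheet is not available and may ask. Only absence from the formal criteria is established.
- **A reader might infer that the results could not show whether the group had cognitive change or fatigue alone.** That does not hold. MoCA and the MFSI mental subscale are collected at Visit C and can be reported.
- **A reader might infer that misclassification must dilute the contrast, or that power is shown to be inadequate.** Neither follows. The direction depends on k. At the plan's uncorrected alpha, the eight listed targets with at least 80% power at 32 per group all keep it at 20% misclassification with k = 0 under the equal-variance formula.
- **A broad fatigue criterion is defensible in a pilot.** True, but then the label should say what the criterion selects.

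**Conclusion.** Both points hold on the text. The statistical section and the inclusion list define the PASC group differently and must be reconciled. As written, the listed criteria can also admit fatigue of other origin under the PASC label.

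The effect on the Aim 4c contrast is unknown in direction and size. The power and false-positive figures are illustrations. They rest on assumed misclassification rates, 32 per group, independent normal data and uncorrected alpha. The plan promises a multiplicity correction but names no method. The figures do not cover the contrast with in-house and published data, whose group sizes are not given. The main cost is what the group label means, not lost power. The change should be made, though the study could run without it.

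**What to change.** 1. **Onset.** Add to PASC inclusion criterion 4: *and this fatigue began or worsened after the index COVID infection*. Ask it at the existing phone pre-screen. Record the answer at the screening history, including when a recent clinical history is substituted.
2. **Group description.** Replace the parenthesis in Statistical Considerations with *PASC subjects who meet the inclusion criteria*. Do not add a completion condition. Microbiome samples are tied to Visit A, and a completers-only group would drop subjects with usable samples who do not return for Visits B and C. Everyone with an evaluable sample should be analysed, and 32 completed subjects should remain only an enrolment target.
3. **Cognition.** Treat MoCA and the MFSI mental subscale as outcomes and report them for the group. If altered cognition is truly meant as an entry condition, list it among the inclusion criteria instead, with an instrument and cut-off.

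**Cost.** One eligibility clause, one pre-screen question and one reworded phrase. Onset will rest on recall at least 6 months after infection, and some extra pre-screen failures are likely (number unknown). The change covers the PASC group only. The control criteria contain no symptom item, and this fix does not address that.
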